10.0 Data and Specimen Banking-N/A

10.1 If data or specimens will be banked for future use, describe where the specimens will be stored, how long they will be stored, when they will be destroyed (if ever), how the specimens will be accessed, and who will have access to the specimens.

10.2 List the data to be stored or associated with each specimen.

10.3 Describe the procedures to release data or specimens, including: the process to request a release, approvals required for release, who can obtain data or specimens, and the data to be provided with specimens, including whether those data will be identifiable to others.

11.0 Data and Specimen Management

11.1 Describe the data analysis plan, including any statistical procedures.

Subjective VMS: As described in the determination of eligibility based on VMS entry criteria section for six months following the intervention, intensity of daytime VMS will be calculated as follows: Intensity = Frequency*Severity = [(frequency of mild*1)+(frequency of moderate*2)+(frequency of severe*3)+(frequency of very severe*4)] and used as a secondary endpoint. Frequency of night sweats will also be recorded daily via self-report the following morning. Baseline VMS frequency will be calculated as the mean of the daily count totals on diaries during the first two screening weeks. VMS frequency at Months 1 to 6 will be calculated as the mean of the daily count totals reported for the 30 days before each visit.

Objective VMS: At baseline, and the 3- and 6-month post-intervention visits, participants will complete a second measure VMS objectively using the ambulatory sternal skin conductance monitor (Biolog Model 3991 x/2-HFI). Raw objective hot flash data will be analyzed by a combination of automated computer software and two trained data coders. According to standard procedures, once an objective hot flash will be coded, no other VMS will be coded for the next 15 minutes. Data will be independently double-scored and double-entered into the database by coders blinded to treatment assignment. Participant sensitivity to objective HF will be calculated by dividing the total number of true positive hot flashes (i.e., objectively determined hot flashes that were subjectively detected) by the sum of the total number of objectively measured hot flashes (i.e., true positives and false negatives). Primary outcome measures will be total objective and subjective hot flashes in a 24-h period, during waking hours, and during sleeping hours.

Title: SGB CA Study

Baseline characteristics: (e.g., sociodemographic variables, primary and secondary outcomes) will be compared between treatment groups using t-tests or chi-square tests for categorical variables. Multiple types of measurement outcomes (frequencies, counts, continuous and incidence outcomes) will be collected in this study. We will conduct intent-to-treat (ITT) analyses for all primary and secondary outcomes using a series of generalized mixed-effects regressions as described below. All statistical tests will be two-sided with significance set at $p \leq .05$. SAS statistical software version 9.2 (SAS Institute Inc., Cary, NC, USA) will be used for statistical analyses. In preliminary analysis, the distributional aspects of the variables under consideration will be examined through descriptive statistics. These statistics will include measures of location (mean, median, quartiles) and measures of dispersion (range, standard deviation, variance) for continuous variables and frequencies of the levels of categorical variables. These measures will also assist with a data cleaning/screening procedure to eliminate any possible copying, handling, recording or measurement errors.

In addition to the features described above, the dependence of outcome measures will need to be properly accounted for in the data analysis as measures will be made at multiple times for the same participant. Consequently, these observations tend to be correlated and require statistical techniques that can properly account for the correlation in order to draw valid inference. Our general approach for analyzing these multiple types of data in this trial will be the Generalized Linear Mixed-Effect Models (GLMM). These models can accommodate a wide range of outcomes including normal, binary, ordinal, and Poisson outcomes, while taking into account correlations from within-subject observations. To study the changes in outcomes over time and to evaluate group differences in these changes, we will construct GLMM models. The main independent variables in statistical model specifications typically include the group indicator, dummy variables for time, and the interactions between them, after controlling for observed and relevant covariates. By properly constructing GLMMs, a wide range of scientific hypotheses can be tested, including cross-sectional differences among groups, the effect of treatment over time and differences between groups over time.

Data will be analyzed using the PROC MIXED, PROC GLIMMIX and PROC NLMIXED in SAS statistical software version 9.2. For the correlation between changes in objective VMS and changes in memory performance, we propose to examine the correlation between frequency of total objective VMS and verbal learning by conducting Pearson correlations to examine associations between changes in cognitive performance and changes in VMS. We will conduct partial correlations to examine whether these associations remained significant after controlling for changes in sleep quality (PSQI and actigraphy-based measures).

11.2 Provide a power analysis, if necessary.

A sample size of 18 in each treatment group will provide at least 80% power to test the two-way interaction between Treatment and Time with a significance level set at 0.05.

Title: SGB CA Study

We will need to screen and enroll approximately 50 women to randomize 36 women. Some women may not qualify due to insufficient number of hot flashes or there may be some withdrawals.

11.3 Describe the steps that will be taken to secure the data to maintain confidentiality (e.g., training, authorization of access, password protection, encryption, physical controls, certificates of confidentiality, and separation of identifiers and data) during storage, use, and transmission

Research files and case report forms will be stored in the research offices of [name] and will be kept in locked offices with access only to the research team. Wherever possible, subject data will be stored using only the study ID. Measures will be taken to protect all personal information and data, including keeping all data sheets under lock and key and entering data into a database that requires login identification and a password made available only to immediate study personnel. The entire study team has taken the CITI training and is familiar with confidentiality requirements and procedures.

Downloaded data from the Biolog hot flash monitor and the actigraph watch will be processed, stored, and analyzed in password-protected network at the University of Illinois in Chicago of [name]. Data related to cognitive assessments will be stored and analyzed at the University of Illinois at Chicago in [name] lab.

11.4 Describe any procedures that will be used for quality control of collected data

A computer-generated 1:1 block randomization scheme will be used to assign participants to receive either a SGB with bupivacaine or a sham injection with saline. Randomization will be performed by [name] immediately before the injection procedure by opening an opaque envelope to reveal the participant number and group assignment printed on an index card. Randomization assignment will be kept under lock and key. Participants and all other study personnel, including those who will perform follow-up evaluations, will be blinded to group assignment. To ensure that [name] knowledge of randomization assignments does not influence study results, he will have no additional follow up or interaction with study participants, unless an adverse event occurs that requires his immediate attention. The study team will be briefed on the types of adverse events that require his attention. [name] will not be involved in the collection of any primary or secondary data outcome.

11.5 Describe how data and specimens will be handled study-wide: see Section 11.0 Data and Specimen Management

11.6 What information will be included in that data or associated with the specimens?

See Section 11.0 Data and Specimen Management

- Where and how data or specimens will be stored?***

See Section 11.0 Data and Specimen Management

- How long the data or specimens will be stored?***

Title: SGB CA Study

Data will be stored indefinitely.

- ***Who (role on the study) will have access to the data or specimens?***

See Section 11.0 Data and Specimen Management

- ***Who (role on the study) is responsible for receipt or transmission of the data or specimens?***

[name] at NU and [name] at UIC are responsible for the receipt or transmission of data. They may designate a member of the research team to transmit data in accordance with NU/UIC IT security policies.

- ***How data and specimens will be transported?***

See Section 11.0 Data and Specimen Management

Provisions to Monitor the Data to Ensure the Safety of Subjects

11.5 Describe:

- ***The plan to periodically evaluate the data collected regarding both harms and benefits to determine whether subjects remain safe. The plan might include establishing a data monitoring committee and a plan for reporting data monitoring committee findings to the IRB and the sponsor.***

The study team will meet and review all adverse events after five subjects have been randomized and received the SGB procedure or sham. Per NU IRB protocol, all UPIRSO's or PRNCs will be reported as soon as the PI becomes aware of it. As the PI is the injectionist, the likelihood of missing a UPIRSO is highly unlikely. If no SAEs/UPIRSO's are observed, the team will meet again after 10 subjects have been randomized. No UPIRSOs or SAEs have occurred in previous studies.

- ***What data are reviewed, including safety data, untoward events, and efficacy data?***

Participants who undergo the SGB with bupivacaine will experience a temporary sympathetic block of the right upper extremity and right face. Efficacy of the SGB will be confirmed by the presence of Horner's syndrome (miosis, abnormal contraction of the pupil; ptosis, drooping upper eyelid; and anhydrosis ,absence of facial sweat) and a temperature increase of the affected extremity, the latter the result of regional venodilation. The temperature of the right upper extremity will be monitored prior to and 30 minutes following the injection to confirm, along with a Horner's syndrome, successful SGB. These events are expected and confirm correct SGB placement. Events outside of those expected are what will be reviewed as stated above. The study team will be trained on the types of study related SAEs or AEs that should immediately be reported to the PI/IRB since they will not have access to the procedures records to maintain the blind.

- ***How the safety information will be collected***

Safety data will be collected with case report forms, at study visits, and by telephone calls with participant.

- ***The frequency of data collection, including when safety data collection starts.***

Title: SGB CA Study

Safety data is collected as soon as the participant agrees to participate and signs the informed consent document.

• ***Who will review the data?***

The PI will review the data with the study coordinator.

• ***The frequency or periodicity of review of cumulative data.***

Efficacy data will be reviewed at the conclusion of the study. Safety data will be reviewed after 5 are randomized, then after 10 are randomized. Thereafter, safety data will be reviewed every 6 months provided that no UPIRSOs are observed in those that have received the study procedure.

• ***The statistical tests for analyzing the safety data to determine whether harm is occurring.***

No statistical test will be used to determine whether harm is occurring. There is a preponderance of safety information on the SGB procedure that is familiar to the PI as this is his area of expertise. If the PI determines that unexpected SAEs and AEs are occurring in the SGB which is higher than seen in clinical practice, he will immediately cease enrollment and notify the IRB.

• ***Any conditions that trigger an immediate suspension of the research.***

A participant study related death will trigger an immediate suspension of the research.

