3.0 Inclusion and Exclusion Criteria

3.1 Describe how individuals will be screened for eligibility.

Patient entry, exclusion and dropout criteria:

a. General inclusion criteria include

1. aged 30 to 75 years
2. 28 or more reported moderate-to-very severe hot flashes per week
3. a minimum of two weeks of VMS diary recording prior to SGB
4. current use of tamoxifen, aromatase inhibitors, or SERMs for a breast cancer indication for at least six months

Title: SGB CA Study

5. willingness to undergo fluoroscopy-guided SGB or sham treatment.
6. if participant is on an SSRI or SNRI, they must be on a stable dose of SNRI or SSRI for previous six month
7. approval of treating psychiatrist or psychologist to participate in study if Depression and Anxiety Scale Score (DASS) score is ≥ 21 for depression or ≥ 15 for anxiety

b. General exclusion criteria include:

1. conditions that preclude SGB or sham intervention (e.g., anatomic abnormalities of the anterior neck or cervical spine; goiter, cardiac/pulmonary compromise; acute illness/infection; coagulopathy or bleeding disorder; allergic reactions/contraindications to a local anesthetic or contrast dye);
2. use of treatments in the past two months that can affect VMS (e.g., use of oral or transdermal HT or contraceptives,
3. conditions or disorders that can affect performance on cognitive tests (e.g., dementia/mild cognitive impairment; stroke; traumatic brain injury; alcohol/substance use; inability to write, speak, or read in English, English as a second language
4. Mini-Mental State Exam (MMSE) ≥ 28
5. conditions that can affect sleep quality (e.g., use of sleep agents; shift work; etc.)

3.2 *Describe the criteria that define who will be included or excluded in your final study sample.*

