After participants have reviewed and signed the consent form in person, they will be interviewed to determine candidacy for the study. They will be asked to provide information about themselves and their medical history. Before the intervention procedure, they will be asked to maintain a diary of VMS. Participants will be instructed to record the frequency and severity of each hot flash or night sweat using the following definitions: “mild” (< 5 minutes, warm, red face, uncomfortable), “moderate” (< 15 minutes, warmth involving neck, ears, head, whole body, with perspiration, clammy skin, dry mouth, tense muscles, tachycardia, irritation, agitation, embarrassment), “severe” (< 20 minutes, warmth described as a raging furnace or burning up, weak, faint, headache, chest heaviness, extreme perspiration, prickling sensation over skin, heart irregularities, anxious, panic attacks) or “very severe” (< 45 minutes, boiling eruption, rolling perspiration, inability to breathe, faint/dizzy, leg/foot cramps, heart irregularities, difficulty functioning, distressed, nausea). They will be asked to do this for a minimum of two weeks prior to the procedure in order to determine eligibility for the study. VMS eligibility will be re-assessed 24 hours before the SGB. A participant will not be permitted to proceed with the initial procedure if they do not have the completed written

Title: SGB CA Study

baseline diary for a confirmatory VMS frequency and severity count at the time of the procedure.

To screen for depression, we will use the Depression Anxiety and Stress Scale (DASS). Women excluded on the basis of their DASS (≥ 21 for depression and ≥ 15 for anxiety) scores will be referred to a mental health provider.

To screen for dementia, we will administer the Mini-Mental State Exam (MMSE). Women with an abnormal or low MMSE score ($MMSE \geq 28$) will be referred to a health provider.

3.3 Indicate specifically whether you will include or exclude each of the following special populations:

The following special populations will not be included in this research:

- *Adults unable to consent*
- *Individuals who are not yet adults (infants, children, teenagers)*
- *Pregnant women*
- *Prisoners*

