Before having the SGB procedure participants will be asked to maintain a daily paper diary of their hot flashes, recording the number and severity using a scale that will be provided to them. They will be asked to do this a minimum of two weeks prior to the SGB procedure in order to determine if they are eligible for the study. They will also record any comments about the hot flashes they experience each day.

At the end of two weeks, a member of the study team will telephone to ask how many hot flashes they are experiencing in a week. If they qualify based on the total number of hot flashes, they will be scheduled to return to the research office for placement of the hot

Title: SGB CA Study

flash monitor, actigraph watch, questionnaire completion and cognitive testing procedures which are described separately.

The study procedure with [name] in the Department of Anesthesiology will be scheduled to occur at a separate visit.

Visit 2 (2 to 3 weeks after visit 1)

There are four types of research evaluations that they will be asked to complete: questionnaires, hot flash monitoring, actigraph watch monitoring and tests of mental abilities (cognitive testing). They will be asked to complete these four tasks at three time points: before the procedure, three months after the procedure, and six months after the procedure. Below we describe each of these types of research evaluations.

Cognitive Testing

They will be asked to complete some memory functioning tests that will assist us in the evaluation of the results of the study procedure. At each session, they will meet one-on-one with a research assistant who is trained in giving tests of different mental abilities. That assistant will instruct the participant on how to complete tasks that measure different mental abilities, such as memory, concentration, and language. Assessment of cognitive function has certain exclusion criteria. If they are found to be ineligible to participate in this portion of the study, they may still participate in the hot flash portion of the study.

Questionnaires

They will also complete questionnaires about mood and everyday functioning. They may refuse to answer any question that they don't wish to answer. If they become uncomfortable at any time and wish to stop, the tests will be stopped. These forms are:

- Depression Scale (CES-D)
- Depression Anxiety and Stress Scale (DASS)
- Mini-Mental State Exam (MMSE)
- McCoy Female Sexuality Questionnaire (MFSQ)

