- Modified Pittsburgh Sleep Quality Index (PSQI)
- Functional Assessment of Cancer Therapy (FACT-B)
- Pain Intensity and Interference Scale (PEG)

Hot Flash Monitoring

A research assistant will attach a hot flash monitor to the participant after they have completed the above mentioned. The hot flash monitor will be returned 24-hours later to the office via UPS or, at their convenience, a research assistant can meet them to disconnect and collect the hot flash monitor at their doctor's office or back at the study site.

Title: SGB CA Study

The hot flash monitor we are using in this study is a small, lightweight, portable recorder that measures how many hot flashes you have each day. The monitor includes some wires and adhesive pads. The adhesive pads are attached to the skin on the chest just below the collarbones. Inside each adhesive pad is a small device that measures hot flashes. Wires send signals from the device to the monitor. Occasionally, the device may malfunction if the adhesive loosens or for other unknown reasons. Should this occur, they may be asked to wear the monitor for an additional 24 hours in order to collect missing objective hot flash data. The monitor measures 1 x 4 x 6 inches and weighs 8 ounces. The monitor is carried in a bag that is worn around the waist like a fanny pack. They will be given verbal instructions and handouts describing how to use the monitor.

Actigraph Watch

The research assistant will also instruct the participant on how to wear an Actigraph. An Actigraph is worn just like a watch and monitors sleep and wake habits. It should be removed for bathing, showering or swimming. They will be given verbal instructions and handouts describing how to use the actigraph watch. They will be given a prepaid return mailing box so that they can return the hot flash monitor and the Actigraph to us via UPS. Visit 3 (4-5 weeks after visit 1)

Stellate Ganglion Injection Procedure

Participants will be interviewed to assess health status and a brief physical exam will be performed by [name]. If they are determined to be a candidate for the procedure by [name], will randomize the participant into one of two groups: one group will receive the study procedure (stellate ganglion injection with local anesthetic or numbing medication) and the other will receive a sham procedure involving a saline injection in the superficial tissues of the right side of the neck in the region just below the skin layer.

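### Section 11.1 builds baseline hot-flash frequency from the first two screening weeks only, leaving the 2–3 weeks of diary nearest the injection unused and the baseline noisier than it need be

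*Combined protocol and SAP*

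**What the plan says.** Section 11.1 (Subjective VMS) fixes the reference level: "Baseline VMS frequency will be calculated as the mean of the daily count totals on diaries during the first two screening weeks". Follow-up frequency in the same paragraph is the "mean of the daily count totals reported for the 30 days before each visit". The baseline sentence covers frequency only; no baseline window is given for intensity.

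The run-in is longer than two weeks. Section 3.1 requires "a minimum of two weeks of VMS diary recording prior to SGB" and a count of "28 or more reported moderate-to-very severe hot flashes per week". In section 9.2, once two weeks have passed, staff "will telephone to ask how many hot flashes they are experiencing in a week". Visit 2 follows 2–3 weeks after visit 1, and the injection comes at "Visit 3 (4-5 weeks after visit 1").

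Section 3.2 re-assesses eligibility 24 hours before the block, and no woman proceeds without the completed "baseline diary for a confirmatory VMS frequency and severity count at the time of the procedure". The look-back period for that re-check is not given.

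Section 8.1 makes reduction in diary-recorded hot flashes the primary endpoint. Sections 11.1 and 11.2 test it as a Treatment x Time interaction with 18 women per group.

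**The concern.** The baseline window closes 2–3 weeks before treatment, is less than half as long as each follow-up window, and is the same fortnight that decides who qualifies. The protocol calls the diary presented at the procedure the baseline diary, yet the analysis takes only its first 14 days.

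Two things are at stake. The first is precision. Baseline error enters every change from baseline and weakens any baseline adjustment, and with 18 women per group there is little to spare. Section 11.2 states its power without an effect size or SD, so the documents show no margin that would make the loss harmless. The second is interpretation. Women admitted on a high count tend to record lower counts later without any treatment, so a within-arm percentage fall overstates what the procedure did.

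**Working it through.** **The plan's own figure.** Section 11.2 claims at least 80% power with 18 per group at 0.05. No effect size, SD, within-woman correlation or dropout rate is given, so the figure cannot be reproduced. Solving backwards (two-sided, normal approximation), the standardised difference must be (1.960 + 0.842) × √(2/18) = 2.802 × 0.333 = 0.93, or about 0.96 with a t-test. Below, the effect is set so that the planned 14-day baseline has exactly 80% power. If another baseline shrinks the SD by a factor r, power becomes Φ(2.802/r − 1.960).

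**Gap.** If the diary starts at visit 1, the window ends at week 2 and the injection is at weeks 4–5: 4 − 2 = 2 to 5 − 2 = 3 weeks.

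**Length alone.** With independent daily noise, the variance of a mean is proportional to 1/days. A 14-day mean therefore has 28/14 = 2.0 to 35/14 = 2.5 times the variance of a 28–35-day mean, and 30/14 = 2.1 times that of a 30-day follow-up mean.

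**Change score, daily noise only (upper bound).** Variance of change is proportional to 1/(baseline days) + 1/30.
- 14 days: 0.0714 + 0.0333 = 0.1048
- 28 days: 0.0357 + 0.0333 = 0.0690; SD ratio 1/r = √(0.1048/0.0690) = 1.232; power Φ(3.451 − 1.960) = 93%
- 35 days: 0.0286 + 0.0333 = 0.0619; 1/r = 1.301; power Φ(3.645 − 1.960) = 95%

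**Change score with slow drift (assumed).** With a day-to-day SD of 2.5 flashes, drift SD of 1.0 on a 14-day scale and a 28-day baseline, the SD of change falls from 1.444 to 1.308 and power is 87%. Across day-to-day SDs of 1.5–3.5, drift SDs of 0–1.5 and baselines of 28–35 days, power is about 84–95%. With baseline adjustment in place of change scores it is about 83–95%.

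**Women also differ in true change (assumed SD 1.5–3 per day).** The gain shrinks. In the least favourable case the SD goes from 3.27 to 3.22 (1/r = 1.016; power 81%), in the most favourable from 2.60 to 2.42 (1/r = 1.074; power 85%).

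**Baseline-adjusted residual variance (separate simulation).** Assumptions: log-normal rates with median 30–45 per week, week-to-week autocorrelation 0.5–0.9, selection at 28 per week, injection at week 4, outcome the 3-month mean. Residual variance is 1 − r² on the log scale, where r is here the correlation between baseline and outcome.

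| Selection | Setting | Weeks 1–2 | All 4 weeks | Cut |
|---|---|---|---|---|
| Weeks 1–2 only | 1 | 0.501 | 0.394 | 21% |
| | 2 | 0.417 | 0.332 | 20% |
| | 3 | 0.752 | 0.633 | 16% |
| | 4 | 0.411 | 0.306 | 26% |
| Re-check also selects | 1 | 0.530 | 0.437 | 18% |
| | 2 | 0.442 | 0.362 | 18% |
| | 3 | 0.793 | 0.696 | 12% |
| | 4 | 0.437 | 0.340 | 22% |

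The first row corresponds to the correlation rising from √(1 − 0.501) = 0.71 to √(1 − 0.394) = 0.78. A 12–26% cut is worth 18 × 0.793/0.696 = 20.5 to 18 × 0.411/0.306 = 24.2 women per arm in place of 18.

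**Recency alone.** Keeping 14 days but moving them next to the injection gives 80.0–82.7% power in the same drift model. Nearly all of the gain comes from averaging more days.

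**Regression to the mean, no treatment effect.** In the 3-month simulation the apparent fall is 3–12% with weeks 1–2 and 2–10% with all four weeks when only weeks 1–2 select; it is similar under both if the re-check also selects. A second simulation with different variance assumptions gives 0.4–5.6% for the first 14 days and 0.1–2.6% for the last 14. With an enforced re-check (assumed: last 7 days at 4 or more per day) these become 0.4–4.9% and 0.4–5.1%.

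**Bias between arms.** With no treatment effect, 18 per arm and the planned baseline, 12 scenarios gave mean arm differences of −0.05 to +0.10 flashes per day and type I error of 3.7–6.1%. That is consistent with no bias and a 5% test within simulation error.

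**The case against.** The strongest reply is that the primary inference is safe. Selection and ageing of the baseline happen before randomisation and act alike in both arms. That stands: a reader might infer that the chosen window biases the treatment comparison, and neither the design nor the null simulation supports this.

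A reader might also infer that a later or longer window would remove the selection effect. It would not. The all-days window still contains the two qualifying weeks, and the 24-hour re-check may select on later weeks as well. The selection model is itself a simplification: eligibility counts moderate-to-very severe events and is first checked by telephone, whereas section 11.1 averages daily totals with no severity limit.

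Age of the window is a weak argument on its own, at 0 to about 3 power points. Nor does any passage say that per-arm reductions will be used to plan the later grant; Goal 3 refers only to the results of this pilot.

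Continued daily recording after week 2 is implied, not stated. The implication is strong: a daily diary with two weeks as a minimum, a completed diary required at the procedure, and recording for the duration of the study. The diary instructions themselves are among supporting documents that are not available here.

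Finally, every magnitude rests on assumed variances, and the planned mixed model over repeated times is not the one-visit adjustment behind the 12–26%. This limits the figures, not their direction.

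**Conclusion.** The concern holds as a point about precision. Section 11.1 uses 14 days where 28–35 are probably available and compares them with 30-day follow-up means. Under assumed variance components, the full pre-injection diary cuts baseline-adjusted residual variance by about 12–26%, or raises an assumed 80% power to about 81–95%. The range is 81–85% if women differ in true change, which is plausible for a procedure whose effect may vary. The direction was the same in every setting tried; the size cannot be derived from the documents.

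The randomised Treatment x Time test is not biased. Regression to the mean affects within-arm percentages under either window, and changing the window lowers it by a point or two or not at all. Only the between-arm contrast should be read as a treatment effect. This is a cheap improvement, not a defect that threatens the trial's conclusion.

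**What to change.** In section 11.1, define baseline VMS frequency and intensity as the mean over all recorded diary days from visit 1 to the day before the first injection, with a stated minimum number of recorded days (for example 14). Keep the two-week count for eligibility only. State in section 9.2 and, if needed, in the diary instructions that daily recording continues until visit 3. State the look-back period of the 24-hour re-check, and say that within-arm reductions are descriptive. Settle the definition before unblinding.

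The cost is a sentence or two in the protocol and a few more diary days to enter per woman; no extra visit is needed. The drawback is that the window would vary slightly in length between women with the scheduling of the injection, which is why the minimum is needed.
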